10.2 Study procedures

[figure not shown]
10.2.1 Study flowchart

Confidential and Proprietary

This document contains confidential and proprietary information on Smith & Nephew PLC and Smith & Nephew, Inc. and is only available to Smith & Nephew and its manufacturers. Without prior written approval of Smith & Nephew, the content cannot be replicated, printed totally/partially or disclosed in any other way, and anyone must use it as per the requirements, either expressed or implied by Smith & Nephew.

Study Protocol - Device	Smith+Nephew
A Prospective, Multi-center, Randomized Clinical Study to Evaluate the Safety and Effectiveness of Biosure Regenesorb Interference Screw in Arthroscopic Reconstruction of Cruciate Ligaments in Chinese Patients	Study No.: BIOSURE RG.SMD.PMA.2019.01
	Version: V2.0/July 3rd, 2020
	Page 34 of 74

Figure 10.2.1 Schematic diagram of study design

10.2.2 Study procedures

10.2.2.1 Evaluation before enrollment in the study

Prior to initiating any study-related activities on a subject, sites must first perform the following pre-study activities:

- Informed consent must be obtained from each subject entering the study using the EC-approved consent form. Informed consent must be obtained prior to any study activity.
- Inclusion and exclusion criteria will be carefully reviewed to verify subject eligibility.
- All combination drugs associated with AEs or SAEs are recorded after the subject signs the ICF.
- The subject enrollment time is the moment when the device is implanted.

10.2.2.2 Pre-operative study activities

Prior to the operation, the following information must be collected:

Confidential and Proprietary

This document contains confidential and proprietary information on Smith & Nephew PLC and Smith & Nephew, Inc. and is only available to Smith & Nephew and its manufacturers. Without prior written approval of Smith & Nephew, the content cannot be replicated, printed totally/partially or disclosed in any other way, and anyone must use it as per the requirements, either expressed or implied by Smith & Nephew.

Study Protocol - Device	Smith+Nephew
A Prospective, Multi-center, Randomized Clinical Study to Evaluate the Safety and Effectiveness of Biosure Regenesorb Interference Screw in Arthroscopic Reconstruction of Cruciate Ligaments in Chinese Patients	Study No.: BIOSURE RG.SMD.PMA.2019.01
	Version: V2.0/July 3rd, 2020
	Page 35 of 74

- Demographics include:
 - Age at surgery (calculated from date of birth)
 - Gender (male/female)
 - Occupation
 - Height (in cm) and body weight (in kg)
 - Body mass index (BMI)
- Vital signs: pulse, blood pressure, respiration and body temperature
- Physical examination status
- Medical history will be obtained and will include:
 - Previous medical history (HEENT, respiratory, gastrointestinal, hematological, cardiovascular, endocrine/metabolic, musculoskeletal, immunological, neurological, genitourinary, prior surgery, others)
 - Tobacco use and alcohol intake (tobacco use: never used, past use, current use; alcohol intake)
 - Closure of epiphyseal plate
 - Current medical history of knee diseases: time of knee injury, cause of knee injury, conditions of the studied knee side (left/right) and the contralateral knee joint, cause of CL rupture or tear, other combined knee injury, knee degeneration and whether or not to totally excise the medial or lateral meniscus
 - Previous surgeries on the affected knee joint (For surgery history, fracture fixation, arthroscopy, ligament surgery, autologous cell transplantation or other surgery, please specify)
 - Safety events
 - All combination drugs associated with AEs or SAEs are recorded.

In addition, subjects will be evaluated clinically pre-operatively using:

- Lysholm Score
- IKDC Score
- Drawer test

Confidential and Proprietary

This document contains confidential and proprietary information on Smith & Nephew PLC and Smith & Nephew, Inc. and is only available to Smith & Nephew and its manufacturers. Without prior written approval of Smith & Nephew, the content cannot be replicated, printed totally/partially or disclosed in any other way, and anyone must use it as per the requirements, either expressed or implied by Smith & Nephew.

Study Protocol - Device	Smith+Nephew
A Prospective, Multi-center, Randomized Clinical Study to Evaluate the Safety and Effectiveness of Biosure Regenesorb Interference Screw in Arthroscopic Reconstruction of Cruciate Ligaments in Chinese Patients	Study No.: BIOSURE RG.SMD.PMA.2019.01
	Version: V2.0/July 3rd, 2020
	Page 36 of 74

- Lachman test
- Lab evaluation (blood routine, C-reactive protein (CRP), blood biochemistry and coagulation function)
- Pregnancy test
- ECG
- Imaging evaluation
 - X-ray film
 - MRI
 - CT

10.2.2.3 Intraoperative-postoperative (Day 0-5) evaluation

- Inclusion and exclusion criteria will be reviewed against to verify subject eligibility.
- Vital signs
- Collection of information on the operative procedure for each subject including:
 - Surgical time (time from entering and leaving the operating room, from skin open to skin close)
- Use of absorbable screws (specifications, number), femoral screws and tibial screws.
 - Labels of the device components used are to be adhered to the Operative medical record page.
 - Treatment of associated other injuries
- Collection of information on discharge including:
 - Admission date
 - Discharge date
- Lab evaluation (blood routine, blood biochemistry; and examination before discharge)
- Imaging evaluation after the operation
 - X-ray film

Confidential and Proprietary

This document contains confidential and proprietary information on Smith & Nephew PLC and Smith & Nephew, Inc. and is only available to Smith & Nephew and its manufacturers. Without prior written approval of Smith & Nephew, the content cannot be replicated, printed totally/partially or disclosed in any other way, and anyone must use it as per the requirements, either expressed or implied by Smith & Nephew.

Study Protocol - Device	Smith+Nephew
A Prospective, Multi-center, Randomized Clinical Study to Evaluate the Safety and Effectiveness of Biosure Regenesorb Interference Screw in Arthroscopic Reconstruction of Cruciate Ligaments in Chinese Patients	Study No.: BIOSURE RG.SMD.PMA.2019.01
	Version: V2.0/July 3rd, 2020
	Page 37 of 74

- CT
- Safety events
- Device deficiency
- All combination drugs associated with AEs or SAEs are recorded.

10.2.2.4 Surgical operation training

The investigators must make a professional judgment based on indications, surgical techniques and medical history of patients to select the appropriate size of screws, bone tunnels and BIOSURE Driver.

Generally, arthroscopy is carried out via anteromedial and anterolateral incisions in the surgery. Remove residual ACL/PCL tissues and perform arthroplasty with a minimally invasive incision. The tibial and femoral tunnels are drilled and then fixed with or without absorbable screws for grafts.

The patient is in supine position, and undergoes routine anesthesia and disinfection. Adopt the conventional approach. Prepare the graft: The investigator selects a homologous tissue as the graft based on conditions of the patient. Under the arthroscopic monitoring, find the femoral attachment of CL, select an appropriate BIOSURE Driver based on the graft diameter and complete the preparation of femoral tunnel. Find the tibial attachment of CL, select an appropriate BIOSURE Driver based on the graft diameter and complete the preparation of tibial tunnel. Insert the prepared graft into the bone tunnel at both ends, and insert the 1.2 mm Smith & Nephew guide wire when the graft is inserted at an appropriate position. Select appropriate absorbable screws based on bone tunnel length and graft diameter.

Note: When BTB is used as a graft, it is recommended to prepare an insertion point using BIOSURE Driver of an appropriate size + 1.2 mm guide wire. The BIOSURE Driver 1 mm bigger than the screw is required when the bone is relatively rigid. Do not use the Biosure Regenesorb Interference Screw with reverse thread when BTB is used as a graft.

Completely install the screw onto the BIOSURE Driver until the laser mark indicates that the screw is installed to the specified length. Tension the graft with a suitable force, and insert the absorbable screw to the appropriate depth to ensure that the graft has been sufficiently anchored in the bone tunnel. Ensure that the BIOSURE Driver is always parallel to the bone tunnel. Remove the BIOSURE Driver and the guide wire. The operation is completed.

Confidential and Proprietary

This document contains confidential and proprietary information on Smith & Nephew PLC and Smith & Nephew, Inc. and is only available to Smith & Nephew and its manufacturers. Without prior written approval of Smith & Nephew, the content cannot be replicated, printed totally/partially or disclosed in any other way, and anyone must use it as per the requirements, either expressed or implied by Smith & Nephew.

Study Protocol - Device	Smith+Nephew
A Prospective, Multi-center, Randomized Clinical Study to Evaluate the Safety and Effectiveness of Biosure Regenesorb Interference Screw in Arthroscopic Reconstruction of Cruciate Ligaments in Chinese Patients	Study No.: BIOSURE RG.SMD.PMA.2019.01
	Version: V2.0/July 3rd, 2020
	Page 38 of 74

If device replacement/repair is required in the initial operation, the investigators will need to replace/repair the device according to the conventional medical device replacement/repair method (e.g., other safe fixation methods).

10.2.2.5 Study activities of follow-up visit post-op

Subjects should return to hospital for follow-up visit at 6 weeks, 12 months and 24 months postoperatively and evaluated clinically using the following endpoints, and the follow-up information should be record in the medical record. Please refer to Study Visit Schedule for the acceptable follow-up windows.

(1) 6, 12, 24 months after the operation

- Lysholm Score
- IKDC Score
- Drawer test
- Lachman test
- Knee joint condition: whether to require a re-operation, whether to experience tear or rupture again.
- Collect and record any AE since last visit.
- Device Deficiency
- All combination drugs associated with AEs or SAEs are recorded.
- Imaging evaluation
 - X-ray film
 - MRI
 - CT

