10.1.5 Efficacy evaluation method

10.1.5.1 Primary efficacy endpoints

Confidential and Proprietary

This document contains confidential and proprietary information on Smith & Nephew PLC and Smith & Nephew, Inc. and is only available to Smith & Nephew and its manufacturers. Without prior written approval of Smith & Nephew, the content cannot be replicated, printed totally/partially or disclosed in any other way, and anyone must use it as per the requirements, either expressed or implied by Smith & Nephew.

Study Protocol - Device	Smith+Nephew
A Prospective, Multi-center, Randomized Clinical Study to Evaluate the Safety and Effectiveness of Biosure Regenesorb Interference Screw in Arthroscopic Reconstruction of Cruciate Ligaments in Chinese Patients	Study No.: BIOSURE RG.SMD.PMA.2019.01
	Version: V2.0/July 3rd, 2020
	Page 31 of 74

The primary study endpoint is the Lysholm score at Month 12 after operation.

The Lysholm score, a knee scoring system created by Lysholm and Gillqui in 1982 and revised in 1985, has been applied in many international literature articles, and its reliability, effectiveness and sensitivity have been demonstrated in international literature. The Lysholm score is a scoring scale the most commonly used before and after arthroscopic knee surgery. A preliminary assessment can be made for the level of motion of patients with different intensity. The scale evaluates functions of patients based on 8 items: limp, support, interlocking, pain, instability, swelling, stair climbing and squatting. The total Lysholm score is 0-100. Pain and instability account for a higher proportion in this score. The knee functions of patients are considered excellent when the score is 95-100, good when 84-94, fair when 65-83 and poor when less than 65. The measurement takes about 3-5 min. The Lysholm score emphasizes the patient's subjective perception of symptoms and grade dysfunction in combination with the score and the level of daily activity. Studies have shown that the scale is the most reliable for patients undergoing cruciate ligament reconstruction and the difference in score is more significant when it is used to evaluate patients who self-limit activities.

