10.1.6.2 Safety evaluation contents

Safety evaluation includes the following contents:

- Incidence (%) and frequency (number of events) of AEs related to device;
- Incidence (%) and frequency (number of events) of adverse events;

Confidential and Proprietary

This document contains confidential and proprietary information on Smith & Nephew PLC and Smith & Nephew, Inc. and is only available to Smith & Nephew and its manufacturers. Without prior written approval of Smith & Nephew, the content cannot be replicated, printed totally/partially or disclosed in any other way, and anyone must use it as per the requirements, either expressed or implied by Smith & Nephew.

Study Protocol - Device	Smith+Nephew
A Prospective, Multi-center, Randomized Clinical Study to Evaluate the Safety and Effectiveness of Biosure Regenesorb Interference Screw in Arthroscopic Reconstruction of Cruciate Ligaments in Chinese Patients	Study No.: BIOSURE
	RG.SMD.PMA.2019.01
	Version: V2.0/July 3rd, 2020
	Page 33 of 74

- Incidence (%) and frequency (number of events) of device deficiencies;
- Reoperation rate.

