12.1.4 Secondary efficacy endpoints

The secondary efficacy evaluation is based on Full Analysis Set (FAS) and Per-Protocol Set (PPS).

Summary statistics of all other secondary variables will be given based on the nature of variables (continuous or classified variables). For continuous variables, the number of observations, mean, standard deviation, median, minimum and maximum will be reported. For classified variables, the number of observations, frequency and percentage will be reported.

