12.2 Calculation of sample size

12.2.1 Total Sample Size

The primary efficacy endpoint of this study is the Lysholm score at 12 months after operation; the trial is designed as a non-inferiority trial. According to references, the non-inferiority margin is set as 5 in this study. Assuming that the variance in both the investigational group and control group is 9, the difference between two groups is 0, the significance level is set to $\alpha=0.025$ (one-tailed), power $1-\beta=0.80$, the calculation formula of sample size is analyzed by referring to the non-inferiority of quantitative indicator:

Confidential and Proprietary

This document contains confidential and proprietary information on Smith & Nephew PLC and Smith & Nephew, Inc. and is only available to Smith & Nephew and its manufacturers. Without prior written approval of Smith & Nephew, the content cannot be replicated, printed totally/partially or disclosed in any other way, and anyone must use it as per the requirements, either expressed or implied by Smith & Nephew.

Study Protocol - Device	Smith+Nephew
A Prospective, Multi-center, Randomized Clinical Study to Evaluate the Safety and Effectiveness of Biosure Regenesorb Interference Screw in Arthroscopic Reconstruction of Cruciate Ligaments in Chinese Patients	Study No.: BIOSURE RG.SMD.PMA.2019.01
	Version: V2.0/July 3rd, 2020
	Page 47 of 74

$$n_T = n_C = \frac{2(Z_{1-\alpha/2} + Z_{1-\beta})^2 \sigma^2}{(D - \Delta)^2}$$

In which, σ is the standard deviation; D is the mean difference between two groups, which is expected to be detected, $D=uT-uC$; Δ is the non-inferiority margin. At least 51 subjects should be included in each group in order to achieve 80% power, 102 in total. In consideration of 20% drop-out rate, 64 subjects are planned to be included in each group, 128 subjects in total; 12 subjects are planned to be added to increase the success rate of trial, 140 subjects in total and 70 in each group.

The estimation of sample size is completed by using PASS13.

12.2.2 Number of Subjects with Each Disease in Clinical Trial and Reason for Determination

In this trial protocol, it is strictly required that patients should be enrolled in compliance with the inclusion/exclusion criteria. It can be considered that all the patients have the same type of disease, and are not further divided.

12.2.3 In multi-center clinical trial, minimum and maximum number of subjects in each clinical trial institution and justification

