12.3 Significance level and power of the clinical trial

The statistical significance level takes the one-tailed significance level of $\alpha=0.025$, 80% power (1- β).

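### Graft re-tear is recorded at months 6, 12 and 24 but is not a listed endpoint, and no rule covers a month-12 Lysholm score that follows re-tear or revision

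*Combined protocol and SAP*

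**What the plan says.** **Collection.** Section 10.2.2.5 records at 6, 12 and 24 months: "Knee joint condition: whether to require a re-operation, whether to experience tear or rupture again".

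**Endpoints.** Section 10.1.5.1: "The primary study endpoint is the Lysholm score at Month 12 after operation". The secondary list (section 10.1.5.2) holds Lysholm at 6 and 24 months, IKDC, Drawer, Lachman and imaging. The safety list (section 10.1.6.2) holds device-related adverse events, all adverse events, device deficiencies and "Reoperation rate". Re-tear is in none of these lists, nor in the synopsis.

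**Analysis.** For secondary outcomes, section 12.1.4 says "Summary statistics of all other secondary variables will be given based on the nature of variables". Section 10.1.6.1 makes safety descriptive. Under section 12.5, acceptance of the trial rests only on the 95% confidence interval for the month-12 Lysholm difference.

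**Handling of scores.** The FAS takes every randomized subject with at least one effectiveness evaluation (section 12.9.1). LOCF applies when the primary score is missing (sections 12.7 and 12.9.1). The PPS takes subjects who complete the trial without a serious violation (section 12.9.2). Section 10.1.4.4 lists a serious adverse event among the reasons for which an investigator may withdraw a subject, and says follow-up need not continue afterwards. No section says what happens to a month-12 score that follows re-tear or revision.

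**The concern.** The screw's job is to hold the graft while it heals, so loss of the reconstruction is the event a reader of a registration report will look for first. The plan collects it but promises no count by arm and no comparison.

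The primary score is also open to two routes by which such an event can be diluted. A knee revised at month 8 and scored at month 12 gives the score of the revised knee to the screw first allocated. If the same subject is withdrawn instead, LOCF supplies the month-6 score, taken before the failure. Which route applies is left to case-by-case decisions. If failures are more frequent on the investigational screw, either route moves the mean difference towards zero, and in a non-inferiority trial that favours a pass.

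**Working it through.** **1. Inputs from the documents.** Section 12.2.1 fixes the margin: "the non-inferiority margin is set as 5 in this study". It takes 80% power, 20% drop-out, a true difference of zero and a final size of 70 per arm. Its statement on spread reads: "Assuming that the variance in both the investigational group and control group is 9". Section 12.3 gives a one-sided alpha of 0.025.

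**2. The plan's own figure.** n = 2(1.960 + 0.842)² σ² / 5². With σ = 9, n = 50.9, so 51 per arm, as stated. With a variance of 9 (σ = 3), n = 5.7, so 6. The 9 was therefore used as a standard deviation. 51/0.8 = 63.75, giving the stated 64. After 20% drop-out, 70 × 0.8 = 56 per arm remain.

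**3. What happens to the score.** Take a re-tear at month 8, under the rules as written:

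| Course | FAS value at month 12 | PPS |
|---|---|---|
| Stays in, scored at month 12, revised or not | Score as observed | Kept, unless there is a serious violation |
| Withdrawn after the event, no month-12 score | Month-6 score by LOCF, from before the event | Not a completer, so excluded |

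Lysholm is scheduled only before surgery and at months 6, 12 and 24 (study schedule), so no score falls between months 6 and 12.

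**4. Effect on the primary result.** The documents give neither a re-tear rate nor a score loss, so both are assumed. Let k of 56 investigational subjects fail, with a deficit of D points at month 12, no control failures and no other device effect. Write q = k/56.

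- Mean difference: Δ = −Dq
- Variance in the investigational arm: 81 + q(1−q)D²
- SE = √[(81 + 81 + q(1−q)D²)/56]
- Lower limit if the rest of the observed difference is exactly zero: Δ − 1.982·SE
- Chance of passing ≈ Φ[(5 + Δ)/SE − 1.982]; simulation of the t-test gives the same values to within about one percentage point

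| k | D | Δ | SE | Lower limit | Chance of passing |
|---|---|---|---|---|---|
| 0 | – | 0 | 1.701 | −3.37 | 83% |
| 8 (14%) | 10 | −1.43 | 1.764 | −4.92 | 52% |
| 5 (9%) | 15 | −1.34 | 1.794 | −4.90 | 53% |
| 3 (5%) | 20 | −1.07 | 1.804 | −4.65 | 58% |

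One more failure in each of the last three rows takes the lower limit past −5: −5.12 (9 at 10 points), −5.20 (6 at 15) and −5.07 (4 at 20).

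**5. With failures in both arms.** Simulated chance of passing at true re-tear rates of 5% (control) and 15% (investigational), 40,000 runs each:

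| Loss per failure | 56 per arm | 70 per arm |
|---|---|---|
| 0 (full recovery by month 12) | 83% | 90% |
| 10 | 60% | 70% |
| 20 | 31% | 38% |
| 30 | 14% | 16% |

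**6. Precision of a re-tear comparison.** At 5% against 15% with 56 per arm, the 95% half-width is 1.96·√[(0.05·0.95 + 0.15·0.85)/56] = 0.110, or ±11 percentage points (±9.8 at 70 per arm). A two-sided 5% test would have about 42% power at 56 per arm and 50% at 70.

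**The case against.** Failures are not invisible. A re-tear meets the adverse-event definition in section 16.1, revision is counted in the reoperation rate, and an event that leads to hospitalization is reportable as serious under section 16.3.1. The protocol itself links positive Drawer and Lachman findings to ligament injury, and both tests are secondary endpoints. A reader might infer that no analysis would show a re-tear; that goes too far. What stands is that none of these outlets counts re-tears as such, none gives a between-arm interval or enters the success rule, and reoperation rate misses an unrevised re-tear.

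A reader might also treat every re-tear as a failure of screw fixation. Section 10.2.2.5 records the event without its cause, so the rate measures loss of the reconstruction, not screw failure alone.

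Using the observed score whatever happened in between is consistent with the intention-to-treat principle cited in section 12.9.1, and that stands: it is a reason to leave the primary analysis alone. Nor does the plan count a revised knee as a success. The endpoint is a continuous mean with no responder category, and entry of the score as recorded follows from silence, not from a written rule.

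Finally, the primary endpoint does respond. At a lasting 20-point loss and 5% against 15%, the trial passes only 31% of the time at 56 per arm. The masking is strongest where scores largely recover or the deficit is small.

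**Conclusion.** The point holds as a gap in the endpoint list and in the handling of the primary score. Re-tear is collected and not listed, and the two default routes for the month-12 score can both understate it.

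Under the assumptions in the working, 3 to 8 excess failures, depending on the deficit, cut the chance of passing from about 83% to between 52% and 58%. The lower limits in the working might be read as showing that the trial would pass with 8 excess failures. They show that only if the rest of the observed difference is exactly zero; the honest figure is close to an even chance. If scores recover fully by month 12, the pass rate is unaffected by the failure rate. The failure counts and score deficits are assumptions; SD, margin and sample size are the plan's own.

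This is a worthwhile, inexpensive improvement. It does not undermine the primary analysis.

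**What to change.** 1. Add to the secondary endpoints (synopsis and section 10.1.5.2) re-tear or re-rupture of the reconstructed ligament, with or without revision, at 6, 12 and 24 months. Report counts by arm and the between-arm risk difference with 95% CI, without a formal test.
2. State in section 12 that the planned FAS analysis remains primary, and how it treats month-12 scores observed after re-tear or revision.
3. Prespecify one supportive analysis of the primary endpoint. Subjects with re-tear or revision before month 12, including those withdrawn because of it, receive an unfavourable value, for example the worst month-12 score observed in either arm. Report whether non-inferiority still holds.

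The last score before the event should not be used in item 3. With no Lysholm between months 6 and 12, a knee that fails at month 8 would keep its intact month-6 score, and the failure would disappear.

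**Cost.** The data item is already collected, so the change is wording, one table and one supportive analysis. The re-tear estimate will be imprecise at this sample size, and the worst-score value is deliberately harsh, so it should be read beside the primary result and not in place of it.
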